9.3.2. Phase 3 exploratory analysis study population

Inclusion criteria

Patients must meet all of the following inclusion criteria to be eligible for inclusion in the study:

- 1. Patients with a documented diagnosis of NSCLC.
- 2. Patients \geq 18 years of age at initial recorded diagnosis of NSCLC.
- 3. Patients who received treatment with lorlatinib within The US Oncology Network or Non-Network practices during the study identification period.
- 4. During the study observation period, patients observed with at least 2 visits⁴ after the index date-1.

Exclusion criteria

Patients meeting any of the following criteria will not be included in the study:

- 1. Receipt of treatment indicated for another primary cancer or diagnosis of another primary cancer (with the exception of non-melanotic skin cancer), within 5 years of index date-1 will be excluded.
- 2. Patients enrolled in clinical trials prior to receiving lorlatinib during the study ID period (index date-1) will be excluded.

9.3.3. Cohort definitions and stratifications

Separate study cohorts will be considered in all phases of the project.

For Phase 1, results will be presented for all patients who meet study eligibility criteria listed in Section 9.3.1 and stratified by subsequent treatment following alectinib (as described in Section 9.1).

For Phase 2, a sample of patients who received alectinib as front-line therapy (i.e., first treatment administration of alectinib not preceded by any other product for NSCLC therapy) will be selected for chart review and results will be presented for all patients selected for chart review and stratified by subsequent treatment following alectinib.

For Phase 3, the stratifications for Phases 1 and 2 will be replicated for all patients who meet study eligibility criteria with the extended identification and observation period as outlined in 9.3. An additional sample of patients identified for chart review for Phase 3 will be stratified by the specified subsequent treatment groups specified in 9.3.1.

9.3.4. Chart review selection

9.3.4.1. Chart review for Phase 2

Among patients who meet the eligibility criteria defined by the inclusion/exclusion criteria listed in Section 9.3.1, a sample size of approximately 100 qualified front-line alectinib patient charts will be selected to undergo a targeted chart review. In the event the total number of eligible patients following structured data screening exceeds the planned number of charts for review, a random sample will be selected.

During the course of abstraction, patients' eligibility for the study will be verified and some of these patients may be found to be ineligible. A total of up to 150 charts are assumed to be reviewed to identify at least 100 patients who received alectinib as front-line.

9.3.4.2. Chart review for Phase 3 study refresh

Two groups of patients are planned for chart review during Phase 3. The first group includes patients from Phase 2 chart review who had ongoing treatment at the end of the observation period (31 December 2019). These patients will undergo additional follow-up through 31 August 2021.

An additional sample of approximately 100 patients who meet the Phase 3 eligibility criteria and received alectinib as front-line therapy and received subsequent treatment among the following groups will undergo chart review:

- Alectinib → lorlatinib
- Alectinib → crizotinib
- Alectinib → brigatinib
- Alectinib only
- Alectinib \rightarrow chemotherapy (optional)

In the event the total number of eligible patients following structured data screening exceeds the planned number of charts for review, a random sample will be selected.

During the course of abstraction, patients' eligibility for the study will be verified and some of these patients may be found to be ineligible. A total of up to 125 charts are assumed to be reviewed to identify at least 100 patients who received post-alectinib treatment from the above listed priority groups.

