For Phase 2, structured data will be supplemented with a targeted chart review to confirm alectinib and other ALK inhibitor oral drug therapy information and collect additional unstructured data for a sample of front-line alectinib (i.e., first treatment administration of alectinib not preceded by any other product for NSCLC therapy) patients from the eligible study population. Results will be presented for all patients selected for chart review, as well as the subgroups of patients who received a subsequent therapy following alectinib:

- 5. Describe the demographic and clinical characteristics of ALK+ NSCLC patients who received alectinib overall, and stratified by subsequent treatment following alectinib
- 6. Characterize post-alectinib treatment patterns and sequencing of other ALK inhibitors; categorizing type of treatments received after alectinib
- 7. Estimate duration of therapy with alectinib and duration of therapy for post-alectinib treatment
- 8. Examine reasons for treatment discontinuation of alectinib and post-alectinib treatment
- 9. Estimate progression-free survival (PFS) of patients post-alectinib stratified by subsequent treatment (as supported by the final sample size)
- 10. Examine overall survival of patients post-alectinib stratified by subsequent treatment (as supported by the final sample size)

Phase 3: Data Refresh (structured and unstructured data) and Exploratory Analysis (structured data)

For Phase 3, the structured and unstructured data study objectives (Phase 1 and Phase 2) will be updated with additional follow-up time through 31 August 2021..

In addition, patients initiating lorlatinib following FDA approval to end of study period will be identified in structured data and the following exploratory objectives will be examined:

- 11. Identify patients initiating lorlatinib and monitor lorlatinib uptake over time
 - Evaluate demographic and clinical characteristics of patients receiving lorlatinib
 - Characterize lorlatinib treatment sequencing utilization and patterns

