Reason for ALK inhibitor (alectinib, and subsequent treatment) treatment discontinuation	Chart review	Treatment characteristics	Study observation period	Data for alectinib and subsequent treatment discontinuation reason will exclusively come from chart review. Reviewers will be asked to select reason(s) as explicitly documented in patients' charts. If available, reason patients discontinued treatment will be abstracted: Completion of therapy Provider-documented disease progression Death Insurance/cost-related Loss to follow-up Patient preference Toxicity Other No information Reviewers will specify other reasons; these will be reported if any represent >5% of patients.	
ALK inhibitor treatment sequencing	iKM structured data + chart review	Treatment pattern	Study observation period	ALK inhibitor treatment paths (e.g. initiate crizotinib followed by ceritinib, initiate crizotinib followed by alectinib, etc.)	
Front-line alectinib	iKM structured data + chart review	Treatment pattern	Study observation period	First treatment administration of alectinib not preceded by any other product for NSCLC therapy except up to 3 months of chemotherapy and immunotherapy preceding alectinib therapy initiation to classify patient as receiving 1L alectinib	
Clinical outcomes					
Last US Oncology Network visit date	iKM structured data + chart review	Clinical outcomes	Study observation period	Each patient's most recent visit date, prior to or on close of study observation period, in the structured data will be recorded. A visit is defined as a physician encounter with the practice where either treatment is given, or vital signs are recorded. For patients with a death date, this last visit date should occur prior to the death date.	

Table 1. Study variables and operational definitions

Variable	Source(s)	Role(s) in study	Period of measurement	Operational definition
				This will not be reported separately; it will be used in calculating the patient's available follow-up time as a descriptive measure. Available follow-up time = Integer (latest of last visit date or death date – index date +1).7

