9.8.1. Analysis sets

Phases 1 and 2

For analyses performed to meet the Phase 1 objectives, all patients who the meet the eligibility criteria defined in Section 9.3.1 will be considered. The study cohorts will be identified based on subsequent therapy following alectinib. For these analyses, datasets consisting of the structured data elements, plus the LADMF to confirm vitality status, required for the landscape analyses will be constructed.

The Phase 2 (chart review) analyses will be limited to a sample of 100 qualified front-line alectinib patient charts identified from Phase 1. The chart review analysis sets will be constructed from both structured and unstructured data, with the LADMF used to confirm vitality status.

Phase 3

For analyses performed to meet the Phase 3 unstructured objectives, all patients who the meet the eligibility criteria defined in Section 9.3.1 will be considered. The study cohorts will be identified based on subsequent therapy following alectinib. For these analyses, datasets consisting of the structured data elements, plus the LADMF to confirm vitality status, required for the landscape analyses will be constructed.

Phase 3 chart review analyses will include a subset of patients from Phase 2 chart review who had ongoing treatment at the end of the observation period and an additional sample of 100 qualified front-line alectinib patients from Phase 3. The chart review analysis sets will be constructed from both structured and unstructured data, with the LADMF used to confirm vitality status.

Some data elements will be captured with both structured and unstructured data. Since the chart review data are expected to provide a richer source of information, if data are available from both sources for a single patient, then chart review data will supersede what is available in the structured iKM data for the final analysis. To account for this, a final analysis data set will be constructed and used to update the landscape analyses once chart review data are available.

For Phase 3 exploratory analysis, all patients who meet the eligibility criteria defined in Section 9.3.2 will be considered. The study cohorts will be identified based on subsequent therapy following lorlatinib. For these analyses, datasets consisting of the structured data elements will be constructed.

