Descriptive statistics (mean, median) and K-M methodology will be calculated from initiation of alectinib, until evidence of discontinuation for any reason, including but not limited to a treatment stop date, a last alectinib administration date, or evidence of new ALK inhibitor treatment or non-ALK inhibitor treatment. Patients who do not have evidence of discontinuing, starting new therapy, or whose last prescription date is <30 days from the end of the study period, will be censored at last visit date or end of study period.

$$DOT = (\frac{\textit{date of ALK treatment discontinuation - index date} + 1}{30.4375})$$

Progression-free survival: The PFS will be measured from the initiation of alectinib to the date of progression or date of death due to any cause, censoring patients who are still alive at the end of the study observation period and did not progress at the last visit date. Progression will be clinician-noted progression as noted per physician notes only, not by traditional Response Evaluation Criteria in Solid Tumors (RECIST) imaging, as this is impacted by frequency of imaging and may not be assessed the same across groups in daily clinical practice. Patients who did not progress or die will be censored on the study end date or the last visit date available in the database, whichever occurred first. The PFS will be estimated in months using the Kaplan-Meier method with 95% CIs, and summary tables of the number of events and censored patients at 3, 6, 12, 18, and 24 months. PFS will be estimated for the full study population and separately by study cohort. Log-rank tests will be used to explore statistical differences.

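### Phase 3 reopens only Phase 2 charts with treatment ongoing at 31 December 2019, but neither PFS censoring nor chart precedence is tied to how far each chart was read

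*Combined protocol and SAP*

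**What the plan says.** - **Which charts are reopened.** Section 9.3.4.2: "The first group includes patients from Phase 2 chart review who had ongoing treatment at the end of the observation period (31 December 2019". It adds: "These patients will undergo additional follow-up through 31 August 2021". The Abstract and Sections 9.2, 9.6 and 9.8.1 use the same criterion. The other Phase 3 chart group consists of about 100 new front-line patients.
- **What is promised.** Section 8: "the structured and unstructured data study objectives (Phase 1 and Phase 2) will be updated with additional follow-up time through 31 August 2021". PFS is objective 9 of Phase 2, so it is included.
- **Where progression comes from.** Section 9.8.3: "Progression will be clinician-noted progression as noted per physician notes only". Table 1 (Section 9.4) lists chart review as the only source of the progression date.
- **How PFS is censored.** Section 9.8.3: "Patients who did not progress or die will be censored on the study end date or the last visit date available in the database", taking the earlier of the two. Table 1 defines the last visit so that each patient's "most recent visit date, prior to or on close of study observation period, in the structured data will be recorded".
- **Which source prevails.** Section 9.8.1, where both sources hold data for a patient: "chart review data will supersede what is available in the structured iKM data for the final analysis".
- **No later document.** Section 9.8 says there will be no separate SAP, so these rules have to be settled in the protocol.

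**The concern.** A Phase 2 chart patient who was alive, progression-free and off treatment on 31 December 2019 (for example after stopping for toxicity or by preference) is not re-read. The structured data and death sources for that patient still run to 31 August 2021. The censoring rule follows the structured visits, while progression can be seen only in a chart that was last read to 2019. No rule ties either censoring or chart precedence to the date through which a chart was abstracted.

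What is at stake is a one-directional error in the refreshed PFS and, by a separate route, stale treatment records in DOT and in the split between Cohort B and Cohorts C-E.

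**Working it through.** The plan gives no event count, sample-size calculation or PFS assumption for this point, so there is no stated figure to reproduce.

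**1. Data currency for a Phase 2 chart that is not reopened**

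| Item | Source | Known through |
|---|---|---|
| Progression | chart notes only (Table 1; 9.8.3) | 31 Dec 2019 |
| Last visit | defined from structured data; chart also listed as a source (Table 1) | 31 Aug 2021 |
| Death | LADMF and EHR (Table 1) | 31 Aug 2021 |
| Later treatment | structured and chart, chart prevails (Table 1; 9.8.1) | not stated |

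**2. Length of the window.** From 31 December 2019 to 31 December 2020 is 366 days, and to 31 August 2021 a further 243, so 609 days. With the protocol's own divisor, 609 / 30.4375 = 20.0 months. This is the most that one patient can add.

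**3. Who can be affected.** Only patients alive, progression-free and off treatment at 31 December 2019 who have later visits. Index dates from 1 June 2017 to 30 June 2019 put that date 6.05 to 30.98 months after index. Assume uniform entry and exponential PFS with rate λ = ln 2 / median. The share still event-free is then

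(e^(-6.05λ) - e^(-30.98λ)) / (24.93λ).

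For a median of 25.7 months (the alectinib arm of the trial cited in Section 7), λ = 0.02697 and the share is (0.849 - 0.434) / 0.672 = 0.62. Let q be the fraction of these patients who are off treatment. The documents do not give q, so it is varied from 5% to 30%: 0.62 × 0.05 = 3% and 0.62 × 0.30 = 19% of the Phase 2 charts. Over assumed medians of 15, 20 and 25.7 months the simulated range is 2-19%.

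**4. Size if these patients are retained.** Kaplan-Meier simulation with 200,000 patients per setting. Further assumptions: 15% of first PFS events are deaths, which are seen without a chart; median survival after progression is 24 months; visits continue to study end; being off treatment is unrelated to prognosis.

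| Assumed median | q | Full review: median / 36-month PFS | As written | Censored at 31 Dec 2019 |
|---|---|---|---|---|
| 15 | 5% | 15.0 / 0.189 | 15.1 / 0.197 | 15.0 / 0.189 |
| 15 | 30% | 15.1 / 0.191 | 15.5 / 0.237 | 15.1 / 0.191 |
| 20 | 5% | 20.0 / 0.288 | 20.2 / 0.296 | 20.0 / 0.288 |
| 20 | 30% | 20.0 / 0.288 | 21.2 / 0.336 | 20.0 / 0.289 |
| 25.7 | 5% | 25.5 / 0.378 | 25.9 / 0.386 | 25.6 / 0.378 |
| 25.7 | 30% | 25.7 / 0.377 | 28.1 / 0.423 | 25.7 / 0.377 |

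The median shifts by 0.1 month (15.1 - 15.0) to 2.4 months (28.1 - 25.7), and 36-month PFS by about 1 to 5 percentage points, always upward. Censoring at the abstraction cutoff removes the shift under these assumptions.

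**5. Size if these patients are dropped.** Section 9.8.1 describes the Phase 3 chart set as the ongoing-treatment Phase 2 subset plus 100 new patients. Every retained Phase 2 patient would then have been alive and on treatment 6 to 31 months after index by selection, while PFS is still counted from alectinib start. Early failures leave the sample, so the bias is again upward. It was not quantified.

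**6. Precedence.** This is a separate matter, because progression has no structured source to be overridden. Section 9.8.1 also uses the merged file to update the landscape analyses, so the rule reaches these patients whichever chart set is used. Take a patient between lines at the end of 2019 who starts a new therapy in 2020. If the 2019 chart record counts as available data, it could displace the newer structured entry and leave the patient in Cohort B.

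**The case against.** Several points on the other side have force.

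- **Retention is not settled.** Section 8, Section 9.3.3 (Phase 1 and 2 stratifications replicated for all eligible patients) and Section 9.8.3 (PFS for the full study population) imply that these patients stay; Section 9.8.1 can be read as leaving them out. One might infer that unreviewed time will certainly be counted as progression-free. The documents support that only conditionally. The other reading is no remedy, as step 5 shows.
- **The precedence rule does not cause the PFS error.** If a chart-abstracted last visit superseded the structured one, censoring would fall back to 2019 and the excess time would vanish. Table 1 defines the visit from structured data, so this cannot be relied on.
- **The 2020 treatment example is a possibility only.** A chart read to December 2019 contains nothing about 2020, and the rule applies where both sources hold data. The plan does not say whether the absence of a chart entry counts as data.
- **The affected group is easily overcounted.** Assuming exponential alectinib duration with a median of 18-25.7 months, one might infer that 38-49 of 100 charts had stopped, subtract 20-30 with a next therapy, and arrive at 8-29 affected. That count includes patients who had died or already progressed. It also uses a PFS median (25.7) as a treatment duration, and a next-therapy share that Section 9.6 gives for 293 patients not restricted to front-line use.
- **Not everyone off alectinib is frozen.** The plan does not say whether ongoing treatment means alectinib or any therapy, so patients on a later line may be re-read.
- **OS is largely protected.** Deaths come from LADMF and the EHR without chart review.
- **Scale.** About 100 new charts dilute the effect, and PFS by subsequent treatment is descriptive and conditional on sample size.

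**Conclusion.** The concern holds in conditional form. Both readings of the Phase 3 chart set bias the Phase 2 contribution to PFS upward: retention by up to 20.0 months of unascertained time per affected patient, exclusion by selecting on continued treatment. The number affected cannot be determined from the documents. With 5-30% of progression-free patients assumed off treatment, the retained reading raises median PFS in the Phase 2 charts by roughly 0.1-2.4 months, before dilution by the new charts. The figures rest on exponential PFS, uniform entry, visits continuing to study end, and off-treatment status unrelated to prognosis.

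The undated precedence rule is a second, independent gap that could affect DOT and cohort assignment; its size is unknown. The documents do not support the stronger claims that PFS bias is certain, that the precedence rule drives it, or that OS is materially affected. The effect is modest but always in one direction, and avoidable by wording.

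**What to change.** 1. In Section 9.8.1, state that all Phase 2 chart patients stay in the refreshed chart analyses, and define whether ongoing treatment means alectinib or any therapy.
2. In Section 9.8.3 and Table 1, censor PFS at the earliest of study end, last visit and the patient's chart-abstraction cutoff. The cutoff is 31 December 2019 for Phase 2 charts that are not reopened. For these patients, apply it to later deaths as well: otherwise they would contribute PFS events over time when progression is not ascertained. OS continues to use deaths to 31 August 2021.
3. In Section 9.8.1, let chart values supersede structured values only up to that cutoff, with later treatment data taken from the refreshed structured data.

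These changes cost wording and programming only. Censoring at the cutoff still assumes that being off treatment is unrelated to later progression, which should be listed as a limitation.

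An optional alternative is to re-abstract every Phase 2 patient alive and event-free at 31 December 2019. That recovers the promised follow-up, but it means additional chart work. Taking those charts from the 125 planned would reduce the yield of new patients.

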Data Sources: Structured data fields within the iKM EHR database will provide information needed to address most research questions. These data will be supplemented by additional unstructured data collected through chart review for a subset of the study population.

Study size

A preliminary feasibility assessment for Phases 1 and 2 identified 293 patients who were treated with alectinib after 01 November 2017, with approximately half treated in the front-line setting. Approximately 20-30% of these patients received a subsequent therapy after alectinib. It is estimated that approximately 300 patients will be included in the Phase 1 structured data analysis. Targeted chart review for Phase 2 is proposed to occur on 150 patients receiving alectinib to identify at least 100 patients who received alectinib as front-line.

For Phase 3 structured analysis, a preliminary feasibility assessment identified 521 patients who were treated with alectinib from 01 June 2017 through 31 December 2020. Chart review for Phase 3 will include patients who had ongoing treatment at the end of Phase 2 study period, and an additional 125 patients will be targeted to identify 100 new patient who received alectinib as front-line therapy. For Phase 3 exploratory analysis, a preliminary feasibility assessment identified 134 patients who were treated with lorlatinib from 01 November 2018 through 31 December 2020.

The final study population for analysis will be defined after identification and review of the patient population meeting the eligibility criteria in the iKM database. A specific power calculation will not be performed as this is a descriptive analysis.

Data analysis

Descriptive analyses will be conducted to evaluate demographic, clinical and treatment characteristics overall, as well as for each of the study cohorts. Time-to-event outcomes (OS, DOT, PFS) will be assessed using the Kaplan-Meier method with 95% CIs and summary tables. All analyses will be presented for each of the study cohorts and, as supported by the final sample size, stratified by front-line alectinib and non front-line alectinib treatment groups.

Milestones

Interim reports for Phase 1 are expected to be delivered May 2020, with the final study report expected October 2020.

The final report for Phase 3 is expected to be delivered in March 2022.

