9.2. Study Design Phase 3 (study refresh and exploratory analysis)

During the Phase 3 data refresh, patients who have evidence of receiving alectinib during 01 June 2017 and 31 August 2020 will be eligible for inclusion in the study. Patients will be followed longitudinally until 31 August 2021, last patient record or date of death, whichever occurs first.

An overview of the study design for Phase 3 is presented in Figure 2.

Figure 2. Phase 3 data refresh study design

^{*}Last visit = last physical encounter, X = Additional visit or record of death

Phase 3 structured data objectives will be assessed among patients who meet study eligibility criteria as specified in 9.3.1 and stratified by subsequent treatment following alectinib.

Cohort A: All alectinib treated patients (overall population)

Cohort B (Alectinib only cohort): Alectinib treatment ongoing, or discontinued and no subsequent treatment³

Cohort C: Alectinib followed by treatment X (top 3 most frequent)

Cohort D: Alectinib followed by treatment Y (top 3 most frequent)

Cohort E: Alectinib followed by treatment Z (top 3 most frequent)

[figure not shown]
³ Patients with ongoing alectibin treatment, patients who discontinued alectinib and patients who did not have a subsequent treatment may be analyzed as separate cohorts depending on sample size of patients

Two groups of patients are planned for chart review during Phase 3. The first group includes patients from Phase 2 chart review who had ongoing treatment at the end of the observation period (31 December 2019). These patients will undergo additional follow-up through 31 August 2021.

An additional sample of approximately 100 patients who meet the Phase 3 eligibility criteria and received alectinib as front-line therapy and received subsequent treatment among the following groups will also undergo chart review:

- Alectinib → lorlatinib
- Alectinib → crizotinib
- Alectinib → brigatinib
- Alectinib only
- Alectinib → chemotherapy (optional)

Figure 3. Phase 3 exploratory analysis study design

^{*}Last visit = last physical encounter, X = Additional visit or record of death

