9.6. Study size

A preliminary feasibility assessment for Phases 1 and 2 identified 293 patients who were treated with alectinib after 01 November 2017, with approximately half treated in the front-line setting. Of the 293 patients receiving alectinib, 74% (n=217) patients had an ALK result. Approximately 20-30% of the 293 patients received a subsequent therapy after alectinib. It is estimated that approximately 300 patients will be included in the Phase 2 structured data analysis. Targeted chart review for Phase 2 is proposed to occur on 150 patients receiving alectinib to identify at least 100 patients who received alectinib as front-line. In the event the total number of eligible patients following structured data screening exceeds the planned number of charts for review, a random sample will be selected.

For Phase 3 structured analysis, a preliminary feasibility assessment identified 521 patients who were treated with alectinib from 01 June 1 2017 through 31 December 2020. Chart review for Phase 3 will include patients who had ongoing treatment at the end of Phase 2

study period, and an additional 125 patients will be targeted to identify 100 new patient who received alectinib as front-line therapy. For Phase 3 exploratory analysis, a preliminary feasibility assessment identified 134 patients who were treated with lorlatinib from 01 November 2018 through 31 December 31 2020.

The final study population for analysis will be defined after identification and review of the patient population meeting the eligibility criteria in the iKM database. A specific power calculation will not be performed as this is a descriptive analysis.

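### The Phase 3 chart target of 100 front-line patients with post-alectinib treatment contradicts the plan's other statements of it and is out of reach at the only rates given

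*Combined protocol and SAP*

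**What the plan says.** **Section 9.3.4.2** (Section 9.2 is almost identical) describes an additional sample of approximately 100 patients who "received alectinib as front-line therapy and received subsequent treatment among the following groups will undergo chart review". Five groups follow: lorlatinib, crizotinib, brigatinib, "Alectinib only", and optionally chemotherapy. The section ends with the yield: up to 125 charts are to be reviewed "to identify at least 100 patients who received post-alectinib treatment from the above listed priority groups".

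**Section 9.6**, and the Abstract in the same terms, put the target differently: "an additional 125 patients will be targeted to identify 100 new patient who received alectinib as front-line therapy". Section 9.8.1 likewise speaks of 100 qualified front-line patients. None of these three places requires treatment after alectinib.

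**Feasibility figures.** For Phase 3 the Abstract reports an assessment that "identified 521 patients who were treated with alectinib from 01 June 2017 through 31 December 2020", in any line. Section 9.2 sets an earlier cutoff: "patients who have evidence of receiving alectinib during 01 June 2017 and 31 August 2020 will be eligible for inclusion in the study". The only rates come from the Phase 1/2 assessment in Section 9.6: about half of 293 patients were front-line, and "Approximately 20-30% of the 293 patients received a subsequent therapy after alectinib". No Phase 3 front-line share or later-therapy share is given.

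**The concern.** Two things do not fit. First, a patient in the alectinib-only group cannot count towards a quota of patients treated after alectinib, yet that group is listed as one of its sources. Second, the feasibility rates suggest far fewer than 100 new front-line patients with a later treatment.

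This matters because Section 9.3.4.2 is the operative selection rule. Section 9.8 says no separate analysis plan will be written, and Section 9.7 says only that the biostatistician will apply a sampling technique. Sections 9.3.3 and 9.8.4 refer the reader to Section 9.3.1 for the groups, but 9.3.1 lists none. Two analysts could therefore draw different samples. One would take switched patients only and fall short. The other would take about 100 front-line patients, most of them alectinib-only. Objectives 8 to 10 (discontinuation reasons, PFS and OS by next treatment) rest on the size of the switched groups, and the literal sentence overstates that size.

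**Working it through.** **The contradiction.** This part needs no arithmetic. Section 9.3.4.2 asks for later treatment, lists a group without it, and counts 100 with it. The Abstract and Sections 9.6 and 9.8.1 count 100 front-line patients of any kind.

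**The plan's own figure.** The plan does not derive the 100. It implies a chart yield of 100/125 = 80%. The one checkable figure in the Phase 1/2 assessment reproduces: 293 x 0.74 = 216.8, stated as 217.

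**Inputs.** 521 patients (Abstract, Section 9.6); front-line share 0.5 and later-therapy share 0.20-0.30 (Section 9.6, Phase 1/2 set); 100 front-line charts already used in Phase 2 (Section 9.8.1), whose identification period lies inside that of Phase 3.

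**Expected supply** = (N x front-line share - 100) x later-therapy share.

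- N = 521: 521 x 0.5 = 260.5, less 100 = 160.5 new patients. Times 0.20-0.30 gives 32-48. Rate needed for 100: 100/160.5 = 62%.
- N scaled to 31 August 2020, assuming uniform accrual by days: 521 x 1187/1309 = 472.4. Half is 236.2, less 100 = 136.2. Times 0.20-0.30 gives 27-41. Rate needed: 100/136.2 = 73%.
- Ignoring the Phase 2 overlap: 260.5 x 0.20-0.30 = 52-78. Rate needed: 100/260.5 = 38%.

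At the top rate of 30%, the exact binomial chance of at least 100 is about 2e-17 from 160 patients and 0.002 from 260.

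**Sensitivity to the front-line share** (an assumption; scaled values in brackets):

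| Front-line share | New front-line | With later therapy at 20-30% | Rate needed for 100 |
|---|---|---|---|
| 50% | 160 (136) | 32-48 (27-41) | 62% (73%) |
| 70% | 265 (231) | 53-79 (46-69) | 38% (43%) |
| 80% | 317 (278) | 63-95 (56-83) | 32% (36%) |

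Dropping the front-line condition and ignoring the overlap gives 521 x 0.20-0.30 = 104-156, but every statement of the target keeps that condition.

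**Sensitivity to longer follow-up** (rough illustration). Assume exponential times with the 25.7-month median PFS cited in Section 7, so the hazard h = ln 2/25.7 per month. With follow-up uniform from a to b months, the event fraction is 1 - (e^(-ha) - e^(-hb))/(h(b - a)). Split the 160 as 50 uncharted Phase 1/2 patients (half of about 300, less 100) and 110 later starters. The fractions are 0.639 for 26-51 months and 0.397 for 12-26 months. Then 50 x 0.639 + 110 x 0.397 = about 76 progressions or deaths. Deaths cannot lead to a switch. Some patients switch without progression, so 76 is not a strict ceiling.

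**The other wording of the target.** The pool of 136-160 new front-line patients exceeds 125 charts, so 100 front-line patients of any kind is reachable. A random 125 of them would include 125 x 0.20-0.30 = 25-38 with later therapy.

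**The case against.** The best defence is that the sentence is only loosely worded. Three other places omit the post-alectinib condition and two sections list alectinib-only as a sampled group, so the intended sample is probably about 100 front-line patients across all five groups, which the pool can supply. That reading is the more plausible one, and it is why the remedy is a restatement. It does not remove the conflict in the selection rule.

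The second defence is that the rates are old. They come from the Phase 1/2 set, for which planned follow-up ended on 31 December 2019, whereas Phase 3 runs to 31 August 2021. The plan also reports 134 lorlatinib patients by the end of 2020. If 60-100% of them had prior alectinib and fall among the 521, lorlatinib alone is 80/521 to 134/521, or 15-26%. The documents do not give that overlap, but 20-30% is not a safe ceiling. This objection stands. A reader might infer that 100 such patients do not exist in the source population. The documents do not support that, because no Phase 3 rate is stated.

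A reader might also infer that charting alectinib-only patients departs from the described sample. It does not, since that group is listed. Small strata are foreseen too: PFS and OS by next treatment are conditional on sample size, and Phase 2 patients still on treatment are followed further and may add switchers to the full chart set. They do not count towards the additional 100.

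**Conclusion.** The point holds in two parts. The contradiction between the post-alectinib quota, the alectinib-only group and the three other statements of the target is certain and rests on no assumption. The shortfall depends on the rates. At about half front-line and 20-30% with later therapy, about 32-48 new front-line patients would qualify, or about 27-41 under pro rata scaling, against a stated minimum of 100. Higher rates would narrow the gap, but with 160 new patients about 62% would need to have switched. The supportable conclusion is that the literal target is not reachable at the rates the plan gives. It does not follow that the Phase 3 chart review is infeasible, since 100 front-line patients of any kind can be found.

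**What to change.** - In Section 9.3.4.2, state the target as about 100 new front-line patients in total from up to 125 charts, alectinib-only included. Delete the post-alectinib condition from the closing sentence and the matching subsequent-treatment condition in Sections 9.2 and 9.3.4.2, so that they agree with the Abstract and Sections 9.6 and 9.8.1.
- Run a Phase 3 feasibility query to the 31 August 2020 cutoff and state the expected number in each next-treatment group. The Phase 1/2 rates should not be written in as expected counts. They cover any later therapy, including immunotherapy, which is not a listed group.
- Keep the random sample. Taking switched patients first would select on an event after baseline and distort the pooled duration of therapy, PFS and discontinuation results. If switched patients are oversampled, report by group or weight pooled estimates back to the front-line population.

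The cost is a wording change and one query. The stated size of the switched subgroups becomes smaller.
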